## 9.4 Data Sources

Source documents are defined as original documents. The investigator will document patient data in his/her own patient files which will serve as source data for the study. Data are collected from the source documents for each patient in the study, consisting of medical records containing demographic data, medical, treatment and diagnostic documentation and laboratory assessments.

The investigator(s)/institution(s) will permit study-related monitoring, audits, independent ethics committee/- review board (IEC/IRB) review, and regulatory inspection(s), providing direct access to source data documents.

### 9.4.1 Data to be Documented

This observational study covers three documentation periods, see Figure 1. An overview on data to be collected throughout the study is summarized in **Table 2**.

---

Confidential Information

No use or disclose outside AbbVie is permitted without prior written authorization from AbbVie  
Version 3.0. (22. Apr 2015) – Germany V3.0 (17. November 2016)

Page 24 of 63

After the patient has signed the patient authorization form, the following data will be documented in the eCRF, if available from the patient charts based on assessments done in physicians' routine clinical practice.

#### 9.4.1.1 Inclusion documentation

The following will be documented:

- Demographic information
  - Interleukin 28B (IL28B) genotypes
- CHC disease characteristics
  - Year of diagnosis and mode of infection
  - Stage of liver fibrosis
- CHC treatment history
  - Naïve or experienced
  - If experienced, most recent prior therapy and outcome
- Relevant medical history, co-morbidities and co-infections
- Concomitant medication, see 9.4.1.5
- ABBVIE REGIMEN ± RBV
- Laboratory data

Key clinical chemistry	Remarks
▪ ALT (alanine-aminotransferase)	including upper limit of normal (ULN),
▪ AST (aspartate-aminotransferase)	including ULN, AST to platelet ratio index (APRI) and Fibrosis-4 Score/Index (FIB-4)* will be calculated
▪ γ-GT (gamma-glutamyltransferase)	
▪ Total bilirubin	
▪ Albumin	
▪ Creatinine	creatinine clearance # will be calculated
▪ AFP	
Key hematology	
▪ Hb (Hemoglobin)	
▪ Platelets	
▪ Prothrombin time	or international normalized ratio (INR)
Virology	
▪ HCV genotype and subtype	
▪ HCV RNA	quantitative/ qualitative HCV RNA by polymerase chain reaction (PCR) test, see 9.4.1.4
HIV-infected patients only	
▪ CD 4 count (cluster of differentiation 4)	most recent assessment
▪ HIV RNA	in copies/mL

---

**Confidential Information**

\*derived from patient's age, ALT, AST and platelets  
\*by Cockcroft-Gault-Formula based on creatinine, gender, age and weight

- Patient questionnaires, see table 2 and 9.4.1.6

#### 9.4.1.2 During Treatment Documentation

Follow-up visits are scheduled by the physician per routine clinical practice. Likewise, treatment, procedures and diagnostic methods will follow physicians' routine clinical practice.

The following will be documented:

- Laboratory data

Key clinical chemistry

- ALT
- AST
  
- $\gamma$ -GT
- Total bilirubin
- Creatinine

Remarks

including ULN  
including ULN,  
APRI and FIB-4 will be calculated

creatinine clearance will be calculated

Key hematology

- Hb
- Platelets

Virology

- HCV RNA

quantitative/ qualitative HCV RNA PCR test, see 9.4.1.4

HIV-infected patients only

- CD 4 count
- HIV RNA

most recent assessment  
in copies/mL

- Concomitant medication, see 9.4.1.5
- Adherence to ABBVIE REGIMEN  $\pm$  RBV
- Tolerability (sAEs and AEs, see 11.5) and pregnancies (see 11.6)
- Patient questionnaires see table 2 and 9.4.1.6

#### 9.4.1.3 Post-Treatment Documentation

Follow-up visits are scheduled by the physician per routine clinical practice. Likewise, treatment, procedures and diagnostic methods will follow physicians' routine clinical practice.

The following will be documented:

---

**Confidential Information**

- **Laboratory data**

- Key clinical chemistry

- ALT
    - AST
  
    - $\gamma$ -GT
    - Total bilirubin
    - Albumin
    - Creatinine
  - Remarks  
including ULN  
including ULN,  
APRI and FIB-4, will be calculated  
  
  
  
  
  
  
  
  
  
creatinine clearance will be calculated

- Key hematology

- Hb
    - Platelets
    - Prothrombin time
  - or INR

- Virology

- HCV RNA
  - quantitative/ qualitative HCV RNA PCR test, see 9.4.1.4

- HIV-infected patients only

- CD 4 count
    - HIV RNA
  - most recent assessment  
in copies/mL

- **Tolerability (sAEs, see 11.4) and pregnancies (see 11.6)**
- **Patient questionnaires see table 2 and 9.4.1.6**

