**Table 2 - Data Documentation Schedule**

Assessment/ Procedure (only available data to be collected; no diagnostic or monitoring procedures to be applied to the patients apart from those of routine clinical practice)	Baseline	Treatment Period			Post-treatment (PT) Period			
		On-treatment visits	Mid treatment visit for pts receiving 24 weeks of therapy	EoT b	Early PT visit	SVR 12 visit	SVR 24 visit	SVR 48 visit
Patient authorization	X a							
Demographic information	X							
IL28B	X							
Relevant CHC disease characteristics	X							
Liver fibrosis stage	X					X		X
CHC treatment history	X							
HCV genotype and subtype	X							
HCV RNA samples	X	X	X	X	X	X	X	X
Clinical chemistry and hematology	X	X	X	X	X	X	X	X
ABBVIE REGIMEN initiation documentation	X							
ABBVIE REGIMEN adherence		X	X	X				
Concomitant medication	X	X	X	X				
Relevant medical history, co-morbidities	X							
sAE, AE and pregnancy reporting	X	X	X	X	X c	X d	X d	X d
For patients receiving RBV: Evidence, in accordance with local label, that female patient or female partner of male patient is not pregnant	X							
Patient questionnaires: FACIT-F	X	X	X	X		X		X
Patient questionnaire: WPAI	X			X		X	X	
Patient questionnaire: PRISM	X					X		X
Patient questionnaires: PAM-13	X			X				
Patient questionnaire: PSP e (U f )			X		X			
Patient questionnaire: PSP e (U f & S g )		X		X		X		

Abbreviations: EoT = End of Treatment (at Week 12 or 24 or at premature discontinuation),  
PT = Post-Treatment

- a Written patient authorization must be obtained before any data documentation in the eCRF
- b Patients who prematurely discontinue should return to the site to document EoT data
- c Tolerability documentation until PT week 4
- d Pregnancy reporting for patients treated with DAA plus RBV
- e applicable for patients enrolled in the PSP
- f Utilization
- g Satisfaction

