## **9.7.6 Tolerability Analysis**

All tolerability variables will be summarized using descriptive statistical methods for the SP stratified by type of combination treatment and scheduled treatment duration.

All SAEs, non-serious AEs and pregnancy occurrences are to be reported for patients included in the study (see Section 11.0 and 9.2.3). AEs will be coded using MedDRA. The number and percentage of patients with treatment-emergent AEs (i.e. any reported event that begins or worsens in severity after initiation of study drug through 30 days post-study drug dosing) will be tabulated by primary MedDRA SOC and PT. Corresponding summary tables will be provided for all serious treatment-emergent AEs. The tabulation of the number of patients with treatment-emergent AEs by severity and relationship to study drug will also be provided. Patients reporting more than one AE for a given MedDRA PT will be counted only once for that term using the most severe incident for the severity summary table and the most related for the relationship summary table. Patients reporting more than one type of event within a SOC will be counted only once for that SOC.

Additional details of the analysis of AEs will be specified in the SAP.

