#### **4.2.8.3 Adverse Events**

All tolerability variables will be summarized using descriptive statistical methods for the SP stratified by treatment regimen and cirrhosis status and overall.

AEs will be coded using MedDRA. A glossary will show the verbatim terms and the corresponding coded terms used (see Table 13).

The number and percentage of patients with treatment-emergent AEs (i.e. any reported event that begins or worsens in severity after initiation of study drug through 30 days post-study drug dosing including those who are related to the study drug independent of the occurrence and those where the date of onset is missing) will be tabulated by primary MedDRA SOC and PT.

Corresponding summary tables will be provided for all serious treatment-emergent AEs and additional for all non-serious treatment-emergent AEs. In the table of non-serious AEs (that must exclude any SAE) only preferred terms that occurred at a frequency of  $\geq 5\%$  in any treatment group will be displayed (no SOCs will be displayed).

The tabulation of the number of patients with treatment-emergent AEs by severity (AEs by severity [mild, moderate, severe], AEs leading to death, AEs leading to hospitalization) and relationship to study drug will also be provided (ABBVIE regimen, ribavirin, medication error -

paritaprevir/r-ombitasvir, medication error – dasabuvir, ABBVIE regimen withdrawn, ribavirin withdrawn).

Patients reporting more than one AE for a given MedDRA PT will be counted only once for that term using the most severe incident for the severity summary table and the most related for the relationship summary table. Patients reporting more than one type of event within a SOC will be counted only once for that SOC.

The frequency of pregnancies will be displayed as well.

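### Protocol 9.4.1.3 asks for serious AEs only after treatment, which contradicts Table 2 and 9.7.6, so non-serious TEAEs with onset after the last dose may be captured incompletely and inconsistently

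*Protocol*

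**What the plan says.** Collection rules:

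- Protocol 9.4.1.2, on treatment: "Tolerability (sAEs and AEs, see 11.5) and pregnancies (see 11.6"). Section 11.5, to which it points, covers serious and non-serious events.
- Protocol 9.4.1.3, post-treatment: "Tolerability (sAEs, see 11.4) and pregnancies (see 11.6"). Section 11.4, to which it points, sets a collection period for SAEs alone, ending 30 days or five half-lives after the last dose.
- Protocol Table 2, repeated in the SAP's data documentation schedule: the row "sAE, AE and pregnancy reporting" is marked at the early post-treatment visit with footnote c, "Tolerability documentation until PT week 4". At the SVR visits that follow, the mark carries footnote d, "Pregnancy reporting for patients treated with DAA plus RBV".
- Protocol 9.7.6: "All SAEs, non-serious AEs and pregnancy occurrences are to be reported for patients included in the study", with no end date.
- Protocol 11.5: non-serious AEs go to the sponsor through the eCRF, again with no period stated.

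Analysis rules:

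- Protocol 9.7.6 and SAP 4.2.8.3 define a TEAE as "any reported event that begins or worsens in severity after initiation of study drug through 30 days post-study drug dosing". The SAP widens this, "including those who are related to the study drug independent of the occurrence and those where the date of onset is missing".
- SAP 4.2.8.3 also plans a separate table of non-serious TEAEs, showing preferred terms that reach 5% in any treatment group.

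**The concern.** Between 9.4.1.2 and 9.4.1.3 both the event type and the cross-reference change: from serious and non-serious events under 11.5 to serious events under 11.4. A site that reads the two sections together could reasonably conclude that non-serious collection stops with treatment. A site that works from Table 2 would continue to about day 28. The analysis assumes that reporting continues to day 30.

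Tolerability is a stated secondary objective. If practice followed 9.4.1.3, an absence of non-serious events after the last dose could mean that none occurred or that none were asked for, and the TEAE tables would not tell the reader which. The non-serious table is the most exposed, because it rests entirely on the category that 9.4.1.3 omits, and a term just under its 5% display limit could drop out. Protocol 9.7.6 also stratifies tolerability by scheduled duration, and the exposed part of the window is relatively larger for the shorter course.

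**Working it through.** The plan states no figure on this point, so there is none to reproduce. The check compares the rules and then works out how much of the window each leaves open.

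**Inputs.** Treatment lasts 12 weeks (84 days) or 24 weeks (168 days), from protocol 9.2.2. The TEAE window runs to 30 days after dosing (protocol 9.7.6, SAP 4.2.8.3). Table 2 footnote c ends at post-treatment week 4, which is day 28. Section 9.4.1.3 asks for no non-serious AEs after treatment.

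**Length of the TEAE window.** 84 + 30 = 114 days, or 168 + 30 = 198 days.

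**Days not covered for non-serious AEs**

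| Rule followed | Uncovered post-dose days | Share of window, 12 weeks | Share of window, 24 weeks |
|---|---|---|---|
| 9.4.1.3 alone | 30 of 30 | 30/114 = 26.3% | 30/198 = 15.2% |
| Table 2 | 30 − 28 = 2 of 30 | 2/114 = 1.8% | 2/198 = 1.0% |
| Collection to day 30 | 0 | 0 | 0 |

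These are shares of calendar time. To turn them into patients one needs event rates on and off drug, which the documents do not give.

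**Illustration, on assumed rates.** Let p be the proportion of patients with a non-serious AE during treatment of T days, and let the hazard be constant, λ = −ln(1 − p)/T. Let the hazard after the last dose be r·λ. Patients whose first non-serious AE falls in the 30-day tail, and who are missed if nothing is collected there, are (1 − p)·[1 − exp(−30·r·λ)]. If collection stops at day 28 the loss is (1 − p)·[exp(−28·r·λ) − exp(−30·r·λ)]. The assumed ranges are p from 30% to 70% and r from 0 to 1.

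- 12 weeks, p = 0.5, r = 1: λ = 0.6931/84 = 0.00825 per day, and the loss is 0.5 × [1 − exp(−0.2476)] = 0.5 × 0.2193 = 11.0 percentage points. With r = 0.5 it is 5.8 points, with r = 0.25 it is 3.0, and with r = 0 it is 0.
- 24 weeks, p = 0.5, r = 1: λ = 0.6931/168 = 0.00413 per day, and the loss is 0.5 × [1 − exp(−0.1238)] = 0.5 × 0.1164 = 5.8 points.
- Table 2 followed, 12 weeks, p = 0.5, r = 1: 0.5 × [exp(−0.2310) − exp(−0.2476)] = 0.5 × 0.0130 = 0.65 points.

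Over the whole assumed range, following 9.4.1.3 alone loses 0 to about 11 points for 12 weeks and 0 to about 6 points for 24 weeks. Following Table 2 loses at most about 0.7 points. The model concerns patients with any non-serious event. It does not say how many single preferred terms would fall below 5%.

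**The case against.** A reader might infer that the protocol as a whole restricts post-treatment collection to serious events, and hence that non-serious TEAE percentages are too low by an amount that differs between sites. The documents do not support that.

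- Only one bullet in 9.4.1.3 is restricted to SAEs. Section 9.4.1 names Table 2 as the overview of what is collected, and Table 2 includes non-serious AEs to week 4. Sections 9.7.6 and 11.5 require non-serious AEs without limiting this to the treatment period, and 9.3.2 lists them among the secondary variables.
- All sites enter data in one central eCRF with common checks and follow-up for medical plausibility (9.6.1). Its AE form is not in the documents, so neither uniform nor site-varying capture can be shown. Under-counting is possible but not established.
- The 26% and 15% cannot be read as shares of events lost. The top of the illustrated range needs the on-treatment hazard to persist unchanged after the last dose, and the bottom is zero.
- The gap between day 28 and day 30 is negligible in itself.
- Tolerability is descriptive and secondary, and serious and non-serious events are tabulated separately. The rules cover non-serious AEs during treatment, and SAEs have their own post-treatment collection period.

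All of this stands and limits the claim to a risk. It does not remove the contradiction. Table 2 and 9.4.1.3 cannot both be followed for non-serious events after the last dose, and SAP 4.2.8.3 does not acknowledge the difference.

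**Conclusion.** The point holds as an internal contradiction with a possible effect on the non-serious TEAE counts. Section 9.4.1.3 conflicts with Table 2 and 9.7.6, and footnote c is the only place that gives non-serious AEs an end, two days short of the analysis window. What is at risk is confined to non-serious events that begin or worsen after the last dose. The size turns on which rule was applied in practice: close to nothing under Table 2, and every such event under 9.4.1.3. The percentage-point ranges rest on assumed event rates and a constant-hazard model, and serve only to show the order of magnitude. The primary endpoint is unaffected. The point still deserves correction, because it bears on the tables for a stated objective and costs little to resolve.

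**What to change.** **Protocol.** Reconcile 9.4.1.3, Table 2 footnote c and sections 11.4 and 11.5 to one stated collection period for non-serious AEs that matches the 30-day TEAE window. Concretely, name both serious and non-serious AEs in 9.4.1.3, move footnote c from week 4 to 30 days, and state the non-serious period in 11.4 or 11.5. The cost is a few wording changes, a note to sites, and a small amount of extra AE entry.

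**If the data are already collected.** This is the likelier case. Inclusion was planned for about 12 months from November 2015, and the SAP sets the data snapshot for its fifth interim analysis at 18 December 2017, so the 30-day tails would be over if recruitment ran to plan. In SAP 4.2.8.3, keep the 30-day TEAE tables, add a tabulation of non-serious TEAEs with onset on treatment (up to the last dose), and footnote that post-dose non-serious events may be incomplete. State how events with a missing onset date, which the SAP counts as treatment-emergent, enter the added table. The cost is one further table and a footnote.

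Cutting the non-serious definition itself at the last dose is not advised. It would discard events validly collected under Table 2, depart from the protocol's TEAE definition, and give serious and non-serious TEAEs different windows.

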**Table 2 - Data Documentation Schedule**

Assessment/ Procedure (only available data to be collected; no diagnostic or monitoring procedures to be applied to the patients apart from those of routine clinical practice)	Baseline	Treatment Period			Post-treatment (PT) Period			
		On-treatment visits	Mid treatment visit for pts receiving 24 weeks of therapy	EoT b	Early PT visit	SVR 12 visit	SVR 24 visit	SVR 48 visit
Patient authorization	X a							
Demographic information	X							
IL28B	X							
Relevant CHC disease characteristics	X							
Liver fibrosis stage	X					X		X
CHC treatment history	X							
HCV genotype and subtype	X							
HCV RNA samples	X	X	X	X	X	X	X	X
Clinical chemistry and hematology	X	X	X	X	X	X	X	X
ABBVIE REGIMEN initiation documentation	X							
ABBVIE REGIMEN adherence		X	X	X				
Concomitant medication	X	X	X	X				
Relevant medical history, co-morbidities	X							
sAE, AE and pregnancy reporting	X	X	X	X	X c	X d	X d	X d
For patients receiving RBV: Evidence, in accordance with local label, that female patient or female partner of male patient is not pregnant	X							
Patient questionnaires: FACIT-F	X	X	X	X		X		X
Patient questionnaire: WPAI	X			X		X	X	
Patient questionnaire: PRISM	X					X		X
Patient questionnaires: PAM-13	X			X				
Patient questionnaire: PSP e (U f )			X		X			
Patient questionnaire: PSP e (U f & S g )		X		X		X		

Abbreviations: EoT = End of Treatment (at Week 12 or 24 or at premature discontinuation),  
PT = Post-Treatment

- a Written patient authorization must be obtained before any data documentation in the eCRF
- b Patients who prematurely discontinue should return to the site to document EoT data
- c Tolerability documentation until PT week 4
- d Pregnancy reporting for patients treated with DAA plus RBV
- e applicable for patients enrolled in the PSP
- f Utilization
- g Satisfaction

**Confidential Information**

#### 9.4.1.4 HCV RNA Sample

HCV RNA sample – the following needs to be documented:

- **Quantitative HCV RNA by PCR test**
  - Test name and result in IU/mL
  - Lower limit of detection (LLoD) in IU/mL and lower limit of quantification (LLoQ) in IU/mL
  
- **Qualitative HCV RNA by PCR test**
  - Test name and result (positive/negative)
  - LLoD in IU/mL

#### 9.4.1.5 Concomitant Medication

Concomitant medication - the following will be documented:

- Concomitant medication used from the time when the decision is made to initiate treatment with the ABBVIE REGIMEN until after the last dose

It should be verified by the treating physician that concomitant medication can be safely administered with the ABBVIE REGIMEN (including ritonavir) and RBV. Some medications may be contra-indicated, some may require dose adjustments due to potential for drug-drug interactions (DDIs). The investigator or qualified designee should review the concomitant medication(s) labels and screen concomitant medications at each visit for potential DDIs.

#### 9.4.1.6 Standardized Assessment Tools

This study will assess quality of life, patient activation, patient health and work ability using PRO instruments: FACIT-F, WPAI, PRISM, PAM-13, PSP (Utilization), and PSP (Utilization & Satisfaction). Validated translations of these patient questionnaires will be administered.

#### **The Functional Assessment of Chronic Illness Therapy-Fatigue (FACIT-F)**

The Functional Assessment of Chronic Illness Therapy-Fatigue Scale (FACIT-F Scale) is a 13-item questionnaire that assesses self-reported fatigue and its impact upon daily

---

Confidential Information

activities and function. It was developed in 1994-1995 to meet a growing demand for the precise evaluation of fatigue associated with anemia in cancer patients. Subsequent to its development, it has been employed in over 150 published studies including over 40,000 people. Since 1995, studied groups have included cancer patients receiving chemotherapy, cancer patients not receiving chemotherapy, long term cancer survivors, childhood cancer survivors and several other clinical samples including people with rheumatoid arthritis, osteoarthritis, psoriatic arthritis, ankylosing spondylitis, multiple sclerosis, psoriasis, systemic sclerosis/ scleroderma, sarcoidosis, paroxysmal nocturnal hemoglobinuria, chronic obstructive pulmonary disease (COPD), stroke, HIV/AIDS, systemic lupus erythematosus (SLE), hidradenitis suppurativa, Crohn's disease, ulcerative colitis, primary Sjögren's syndrome, Gaucher disease, chronic immune thrombocytopenia, chronic kidney disease, and Parkinson's disease, as well as the general United States population. In all cases, the FACIT-F Scale has been found to be reliable and valid.

The FACIT-F Scale has been used by over 200 investigators from medical and educational institutions, industry sponsors, and cooperative multicenter clinical trial organizations. Applications include use in Phase II, III, and IV clinical trials, in health-practice self-studies; for symptom management, and in other chronic illness treatment evaluations. The FACIT-F Scale is typically used in the clinical trial setting but has also been used in screening, survivorship, and end-of-life evaluations.

The FACIT-F Scale is written at the 4th grade-reading level as measured by the Lexile Framework, and is specifically formatted for ease of self-administration. Respondent burden takes 2-3 minutes for an average patient to complete The FACIT-F questionnaire is presented in Annex 1.

### **Assessment of work productivity and activity impairment (WPAI)**

Assessments of work productivity and activity impairment as assessed by the WPAI Hep C v2.0 will be evaluated according to the WPAI-SHP scoring manual. The WPAI yields four types of scores, the results of which will be presented as percentage of impairment from 0 to 100. Higher percentages indicate greater impairment:

1. % absenteeism: percentage of work time missed due to hepatitis C
2. % presenteeism: percentage of impairment while working due to hepatitis C
3. % TWP: percentage of overall work impairment due to hepatitis C
4. % TAI: percentage of general (non-work) activity impairment due to hepatitis C

---

Confidential Information

The WPAI Hep C v2.0 consists of 6 questions aimed at the following targets:

- Q1. currently employed (yes, no)
- Q2. hours missed due to hepatitis C in the last seven days
- Q3. hours missed due to other reasons in the last seven days
- Q4. hours actually worked in the last seven days
- Q5. degree hepatitis C affected productivity while working
- Q6. degree hepatitis C affected regular activities

The four scores will be derived as follows:

- 1. % absenteeism:  $100 \cdot Q2 / (Q2 + Q4)$
- 2. % presenteeism:  $100 \cdot Q5 / 10$
- 3. % TWP:  $100 \cdot \{Q2 / (Q2 + Q4) + [Q4 / (Q2 + Q4)] \cdot Q5 / 10\}$
- 4. % TAI:  $100 \cdot Q6 / 10$

A score will be set to missing if one or more of the items Q1-Q6 that are needed for the calculation of the score are missing. No imputation will be performed for missing items.

The summary table will present the absolute and relative frequencies of employed and unemployed patients and descriptive statistics for the four scores. Further details of the analysis will be specified in the SAP. The WPAI should require approximately 5 minutes to complete and is presented in Annex 2.

